Secondary objectives: Compare pulmonary hygiene and function amongst patients with non-operatively managed traumatic rib fractures via incentive spirometry scores and incidence of post-traumatic pneumonia and radiological evidence of atelectasis incidence

METHODS AND PROCEDURES

Study Design: *Describe the research design, including a description of any new methodology and its advantage over existing methodologies.*

Per Jeffords Institute for Quality Data, there were 190 patients admitted to the Acute Care Surgery (Trauma) service at the University of Vermont Medical Center during the year 2016. Assuming that these numbers remain fairly static overtime as they have in the past, we would expect approximately 16 patient admissions per month with the diagnosis of rib fracture (seasonal fluctuations do exist with more traumatic admissions during the summer months). The goal time period for the trial would be to conduct this trial during the summer, with a goal of 50 total patients. We would therefore expect an enrollment period (data collection phase) of approximately 3 months.

During the study (following appropriate IRB approval), appropriate patients will be recruited both to the control arm of the study and the intervention/comparison arm in a specified / non-randomized sequence as seen in the schematic below (First 5 patients control, next 5 patients intervention, next 5 patients control, next 5 patients intervention, next 5 patients control, final 25 patients intervention). Control arm will include 15 total patients. All will be consented to the study upon admission (first 24 hours of index hospitalization for injury) with full knowledge that they will either be undergoing no intervention other than receiving the current standard of care for rib fracture care per our institution's standard, and if assigned to the rib belt group, expected to wear the rib belt during their recovery.

The current standard of care for rib fractures at our institution is as follows: includes oral and IV analgesia and other multimodal pain control as appropriate, including muscle relaxants such as methocarbamol (robaxin) unless there is a contraindication, pulmonary hygiene/toilet and respiratory care (including frequent evaluations by physicians, respiratory therapists, and nursing staff, early mobilization, and monitoring for pulmonary complication (via vital signs, pulse oximetry, oxygen requirement, chest imaging if appropriate).

[figure not shown]

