Subjects targeted for the study are those that would benefit most from the intervention (Rib belt)- patients with traumatic rib fractures. In order to determine if the belt has efficacy in this population, we must utilize the belt in this target population. Patients at the extremes of age (<18 or >80 years old) have been ruled out as they may create unreasonable confounding when measuring the relevant study outcomes, as well as potentially creating issues with autonomy and consent processes. There are also other exclusion criteria as dictated below.

Vulnerable Populations: Explain the rationale for involvement of special classes of subjects, if any. Discuss what procedures or practices will be used in the protocol to minimize their susceptibility to undue influences and unnecessary risk (physical, psychological, etc.).

Not applicable

Number of Subjects: What is the anticipated number of subjects to be enrolled at UVM/UVM Medical Center and in the case of a multi-center study, with UVM/UVM Medical Center as the lead, the total number of subjects for the entire study.

The current anticipated number of subjects is 35 patients in the intervention arm, and 15 in the control arm of the study, for a total of 50 patients. All these subjects will be enrolled at UVMMC.

Inclusion/Exclusion Criteria: Eligibility and ineligibility criteria should be specific. Describe how eligibility will be determined and by whom. Changes to the eligibility criteria at a later phase of the research have the potential to invalidate the research.

Inclusion Criteria:

Adult person age 18-80 admitted with at least one acute traumatic closed rib fracture to the University of Vermont Medical Center

Exclusion Criteria:

Pediatric (<18 year old) and Geriatric (>80 year old) patients

Patients who are intubated on arrival or within first 24 hours of admission or with Glasgow Coma Scale (GCS) < 14 (altered or depressed consciousness)

Pregnant patients

Patients who undergo operative rib fixation for their rib fractures (such as open reduction internal fixation, or rib plating)
 Patients with chest wall deformity, lacerations, burns, or soft tissue injuries that preclude placement of the RibFx belt
 Patients with an additional mechanism of injury that would create severe distracting pain, as determined by the admitting team.
 Isolated 1st rib or 2nd rib fractures

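### The 3-month enrolment estimate makes no allowance for exclusions or refusals, and the assignment order leaves the last 25 patients, all belt, without concurrent controls

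*Combined protocol and SAP*

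**What the plan says.** Under Methods and Procedures, Study Design, the protocol reports that "there were 190 patients admitted to the Acute Care Surgery (Trauma) service at the University of Vermont Medical Center during the year 2016" and infers that "we would expect approximately 16 patient admissions per month with the diagnosis of rib fracture". It adds that "seasonal fluctuations do exist with more traumatic admissions during the summer months", gives no size for that increase, and plans to run in summer "with a goal of 50 total patients". From this it concludes: "We would therefore expect an enrollment period (data collection phase) of approximately 3 months".

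The same section fixes a non-random order of assignment: "First 5 patients control, next 5 patients intervention, next 5 patients control, next 5 patients intervention, next 5 patients control, final 25 patients intervention". The Number of Subjects section gives the same totals: "35 patients in the intervention arm, and 15 in the control arm of the study, for a total of 50 patients".

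The Inclusion/Exclusion Criteria remove patients over 80, those intubated within 24 hours or with GCS below 14, pregnant patients, those having operative fixation, those whose chest wall cannot take the belt, those with severe distracting pain, and those with isolated first or second rib fractures. Consent Procedures place consent in the first 24 hours of admission. No eligible or consenting share is given.

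The only power calculation, under Statistical Considerations, is for the pre-post comparison within the belt group: 83% with 30 patients and 88% with 35. That section says the trial is not powered for belt against control.

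**The concern.** The estimate divides the enrolment target by the admission rate, so it treats each admission as an enrolled patient. The protocol's own eligibility and consent rules say that some will be lost, and the plan does not say how many.

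The order of assignment makes this matter more than a late finish usually would. All 15 control places lie within the first 25, and the last 25 are belt only. Two things follow. If enrolment were ever closed short of 50, the loss would fall on the group that carries the power calculation. And whether accrual is fast or slow, the second half of the trial has no controls enrolled beside it, so a belt-control contrast mixes the belt with anything that changes over calendar time, such as season, injury pattern or routine care.

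**Working it through.** **Inputs.** From Study Design: 190 admissions in 2016, target 50, order 5C-5B-5C-5B-5C-25B (C control, B belt). From Statistical Considerations: MPQ PRI mean 28, SD 16, a 20% decrease, within-subject correlation 0.8, two-sided alpha 0.05, target power 80%. Capture (the share of admissions that are eligible and consent) is not in the documents; every value below is an assumption.

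**Reproducing the 3 months.** 190/12 = 15.8 per month. 50/16 = 3.13 months (50/15.83 = 3.16). The stated figure follows if capture is 100%.

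**What 3 months supplies.** 15.83 × 3 = 47.5 admissions against 50 needed, or 50/47.5 = 105% capture (104% with the rounded 16 per month).

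**Summer rate needed for 50 in 3 months**, (50/3)/capture, compared with the stated 16:
- 80% capture: 20.8 per month, 1.3 times
- 70%: 23.8 per month, 1.5 times
- 50%: 33.3 per month, 2.1 times

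**Time to reach 50 at the average rate**, 50/(15.83 × capture): 4.2 months at 75%, 5.3 at 60%, 6.3 at 50%.

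**Reproducing the power.** Difference = 0.20 × 28 = 5.6. SD of the paired difference = 16 × √(2 × (1 − 0.8)) = 10.12. A two-sided paired t-test (noncentral t) gives 83.4% at n = 30 and 88.9% at n = 35, against the stated 83% and 88%. The same calculation is used below.

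**If enrolment closed at 3 months at the average rate.** Totals are 47.5 × capture, rounded down. Arms are counted from the first places of each order; the alternative is five repeats of 3C then 7B.

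| Assumed capture | Enrolled | Stated order C/B | Belt power | 3C-7B blocks C/B | Belt power |
|---|---|---|---|---|---|
| 75% | 35 | 15/20 | 65% | 12/23 | 72% |
| 60% | 28 | 15/13 | 45% | 9/19 | 63% |
| 50% | 23 | 13/10 | 35% | 9/14 | 48% |

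Under the stated order, control is complete at 15 once 25 are enrolled, so for totals of 25 to 49 every missing patient is a belt patient. Power drops below 80% at 42 or fewer enrolled (42 − 15 = 27 belt, 79.0%); at 43 it is 80.6%.

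**Concurrent controls.** The last control occupies place 25 of 50, so 25 of the 35 belt patients (71%) enrol after the last control. This does not depend on the accrual rate. With 3C-7B blocks, controls enter at places 1–3, 11–13, 21–23, 31–33 and 41–43.

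**The case against.** The division is correct: 3.13 months is approximately 3. A reader might infer that the timeline contains an arithmetic error, but what is missing is an allowance for exclusions and refusals.

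A reader might also infer that 50 patients in 3 months cannot be reached. The documents do not show that. Sixteen per month is an annual average, and the plan places the trial in a season it describes as busier. With an uplift of 1.3 to 1.5 times and capture of 70–80%, the target could be met. That is optimistic, and neither figure is given, but it is not impossible. The project timeline chart is also not visible in the text available, and it may show a longer window.

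The strongest objection concerns power. Enrolment is defined by a count of 50, and 3 months is an expectation with no cutoff attached. A reader might infer that the trial will end with 35–65% power. As written, slow accrual simply continues to 35 belt patients and the stated 88%. The lower figures need an early closure that the plan does not contain. This objection stands, and those figures are conditional.

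The missing concurrent controls are a matter of allocation order and would exist even if 3 months were exact. That is also true, and it is why the point does not rest on the timeline alone. The principal aim is within-patient and the belt-control comparison is unpowered, which limits the harm. But the controls are there to show change that occurs without the belt, and they can do that for later patients only if calendar time makes no difference.

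**Conclusion.** The point holds as an unsupported feasibility estimate combined with an avoidable weakness in the assignment order.

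- At the stated rate, 3 months requires essentially all admissions to be enrolled (47.5 available, 50 needed). It becomes plausible only with a summer uplift of about 1.3 times at 80% capture or 1.5 times at 70%, all assumed values.
- Running on to 50 preserves the stated power but, at the average rate and an assumed 75–50% capture, takes about 4.2 to 6.3 months and passes the intended summer window. These durations illustrate the range; they are not corrected estimates.
- Only if enrolment is closed early does the order put the whole shortfall on the belt group (totals of 25–49), with power below 80% at 42 or fewer enrolled.
- Whatever the duration, half the trial has no concurrent controls, so the belt-control comparison is open to calendar-time differences. The documents give no basis for sizing that bias.

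The calculation takes the 190 to be rib-fracture admissions, as the protocol's next sentence does. If it counted all admissions to the service, the rate would be lower and the estimate weaker.

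**What to change.** 1. Replace the order with five repeating blocks of 3 control and 7 belt. Totals stay at 15 and 35 and controls span the whole accrual. The ratio is exact at completed blocks and approximate between them (belt share 14/23 = 61%, 19/28 = 68% and 23/35 = 66%, against 70% planned). If accrual stopped early, this would reduce the loss of belt power without removing it: all three totals in the table stay below 80%. The order would still be fixed and non-random, so it does not address predictability of assignment.
2. Restate the enrolment period from an explicit summer admission rate and an explicit eligible-and-consenting fraction, showing the calculation.
3. State that enrolment continues until 50 patients are enrolled, whatever the calendar.

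The cost is a less favourable stated timeline and a reordered assignment list. No extra patients or assessments are needed.

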Patients determined to be eligible for the study by the patient's clinical provider (and per our previously defined criteria) will be recruited to enroll in the project within the first 24 hours of their hospital admission (i.e. 24 hours following the documented H&P Note). They will be offered the opportunity to consent to enrollment in the study and will be assigned by the study team into either the intervention (RibFx belt +current standard of care) (n=35 subjects) or control (current standard of care) arm (n=15 subjects) in a quasi-experimental prospective design: untreated control group with dependent pretest and posttest samples. In this manner, the intervention arm will be both compared to themselves (pretest vs. posttests) as well as to a control group not exposed to the intervention.

Patients upon enrollment in the study will undergo an initial assessment that will include their baseline pain scores, narcotic

consumption, incentive spirometry scores, and the subjective self-reported results of their questionnaire (the pre-test questionnaire- see attached). Patients will continue to be scored on objective (incentive spirometry results, opioid pain medicine consumption) and subjective variables (pain scores) during their hospital course. Between 24-48 hours after enrollment, they will be prompted to again complete a similar 2nd questionnaire post-test (if they are discharged from the hospital at this point in the time course, they will be sent home with the questionnaire and prompted to complete it at home, or asked for an agreed upon time and day for study staff to call the patient to complete the questionnaire over the phone). At their follow up appointment in trauma clinic (which will be coordinated by the research team to be as close as possible to 3 weeks post injury), they will have the opportunity to again voluntarily complete a final short questionnaires (post-test) that assess their pain control and respiratory function over the last 3 weeks. If the patient does not plan to follow up in trauma clinic (or is not asked to), we will ask the patient for an agreeable time and day to call the patient and administer the questionnaire over the phone. At this point, their involvement in the trial will be complete.

All aspects of data collection will be performed only by approved members of Key Personnel.

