The following additional data will also be quantified from the medical record via manual data extraction: ICU length of stay, hospital length of stay, pulse oximetry and respiratory rate scores (taken from already collected vital signs every four hours), body mass index (BMI), bronchodilator (such as albuterol or other inhaled beta agonist) use, age, sex/gender, tobacco history/pack years, days on mechanical ventilator, narcotic requirement (in mean morphine equivalents or morphine equianalgesic dose per day).

In addition, an independent radiology physician will analyze the chest x-rays, CT chests of the patients enrolled in the study and grade them in a blinded fashion) on a scale for the following characteristics: Degree and quantity of rib fracture, presence and degree of atelectasis, presence of COPD/emphysematous change or other parenchymal lung disease, presence and degree of pneumothorax, bilateral vs. unilateral disease, presence of intrapleural fluid, evidence of "flail chest" segment, and presence of pulmonary contusion and other noted pathology (see the attached Radiology Grading Form document). We will measure the degree of radiological severity and compare the control and interventional group to determine what differences in initial disease severity exist (so they can be accounted for).

GANTT CHART WITH PROJECT TIMELINE FOR RibFx CLINICAL TRIAL

Procedures: Describe all procedures (sequentially) to which human participants will be subjected. Identify all procedures that are considered experimental and/or procedures performed exclusively for research purposes. Describe the types, frequency and duration of tests, study visits, interviews, questionnaires, etc. Include required screening procedures performed before enrollment and while on study. Please provide in table, list or outline format for ease of review. (describe and attach all instruments)

Note: A clinical research protocol may involve interventions that are strictly experimental or it may involve some aspect of research (e.g., randomization among standard treatments for collection and analysis of routine clinical data for research)

(purposes). It is important for this section to distinguish between interventions that are experimental and/or carried out for research purposes versus those procedures that are considered standard therapy. In addition, routine procedures performed solely for research purposes (e.g., additional diagnostic/follow-up tests) should be identified.

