Each patient in the interventional arm will be fitted with a RibFx orthosis belt, which is to be worn during the majority of their day (excluding showering/bathing). It will be encouraged (though not mandatory) to wear at night. Patients in both the control and interventional arm will be expected to participate in pulmonary hygiene / toilet exercises with guided and independent incentive spirometry as per our normal routine and standard of care. There are no other interventions or procedures that the patients will be subjected to for the research trial- other procedures/interventions will be performed only if the clinical care team feels they are indicated.

For research involving survey, questionnaires, etc.: *Describe the setting and the mode of administering the instrument and the provisions for maintaining privacy and confidentiality. Include the duration, intervals of administration, and overall length of participation. (describe and attach all instruments)*

Not applicable

Patients will be assessed with three short questionnaires in a pretest , posttest fashion at both the onset of the study, 24-48 hours after enrollment, and at their follow-up appointment 3 weeks after (2 post test questionnaires). The initial evaluation will occur on initial assessment prior to placement of the rib belt (or, for the control/ non-intervention group, at the onset/first 24 hours of the study).

Each of the questionnaires is essentially the same with only brief modifications made in the first two questions to make them appropriate for the timing during the clinical course. However these are all attached (see Questionnaire 1,2, and 3). Questionnaires 2 and 3 may be facilitated over the phone if the patient is discharged before the defined time frames are met.

Patients in both the intervention and control arms will present in post-admission follow up at a time period of 3 weeks post injury (range, 2-4 weeks) following their hospital admission, and will be asked to fill out a brief survey regarding their respiratory function and pain control. This survey will also inquire into compliance with the use of incentive spirometer, and compliance with the use of the RibFx belt (for patients in the intervention arm). If patients are not asked to present to trauma clinic for follow up, or if a patient does not intend to follow up, we will aim to complete this questionnaire over the phone in the same time frame.

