In this study, we will utilize a quasi-experimental design to compare 35 subjects to themselves in a pre-test, post-test fashion. In addition, we will have an additional 15 non-interventional control patients to observe for temporal changes in patient's symptoms not secondary to the intervention itself. However, it is important to note that the study is not powered to detect differences between the control group and the intervention group. The purpose of the control group is to observe for differences that occur in this population over time regardless of intervention (it should be assumed that pain will improve as time increases from the set injury point, regardless of intervention). Further, this preliminary data could potentially be used to calculate an accurate power calculation for a definitive randomized controlled trial.

Groups will be compared by demographical and clinical data to determine what potentially confounding differences exist between the arms of the study. Relevant objective data that will be used to determine group differences include (but not limited to): age, sex, tobacco use status (active/former/none), presence of asthma, presence of COPD, or presence of restrictive lung

disease, home oxygen use, obstructive sleep apnea/ CPAP use, chronic pain incidence, narcotic/opioid medication consumption, obesity/ BMI. We will also measure relevant variables of their clinical course such as regional block/anesthesia/epidural administration. Radiological appearance of presenting imaging (either CT Chest or chest X-ray) will be compared by a dedicated and blinded radiologist who will grade the initial imaging based on severity including the following variables: number of fractures, bilateral vs. unilateral, degree of displacement, presence of lung contusion, presence of pneumothorax, presence of intrinsic lung disease, pleural effusion or blood.

Survey results (both pretest and posttests) will be compared using the appropriate statistical methods depending on the questions construct: with Chi squared performed for categorical variables (such as multiple choice) and unpaired t test for continuous variables (such as likert scale rankings).

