Patients who are first identified by the clinical care team (The Acute Care Surgery/ACS/ Trauma Surgery team at UVMC) as meeting the desired inclusion criteria for the trial will be offered the opportunity to participate in the trial and appropriate clinical materials will be given by a member of the research team. There will be no advertisements, mailers, or other relevant recruitment materials other than an informational pamphlet, a device pamphlet, and the appropriate consent/authorization forms. These items are attached with the relevant research forms.

FINANCIAL CONSIDERATIONS

Expense to Subject: If the investigation involves the possibility of added expense to the subject (longer hospitalization, extra studies, etc.) indicate in detail how this will be handled. In cases where the FDA has authorized the drug or device company to charge the patient for the experimental drug or device, a copy of the authorization letter from the FDA or sponsor must accompany the application. Final approval will not be granted until the IRB receives this documentation.

There are very limited circumstances under which study participants may be responsible (either directly or via their insurance) for covering some study-related expenses. If the study participant or their insurer(s) will be billed for any portion of the research study, provide a justification as to why this is appropriate and acceptable. For example, if the study involves treatment that is documented standard of care and not investigational, state so. In these cases, the protocol and the consent should clearly define what is standard of care and what is research.

The research team does not anticipate that participation in the trial will result in any additional hospital time or expense. The actual RibFx belt will be provided, free of charge to the patient (actual retail value \$125 USD). All other interventions and modalities will be per the current standard of care for the treatment of rib fractures- patients will continue to be billed for the rest of their hospital care. In that (expectedly) extreme rare event that at any point during the trial it became apparent that the device has caused a medical complication necessitating additional treatment, this medical care will be provided without billing the patient for those services.

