Payment for participation: Describe all plans to pay subjects, either in cash, a gift or gift certificate. Please note that all payments must be prorated throughout the life of the study. The IRB will not approve a study where there is only a lump sum payment at the end of the study because this can be considered coercive. The amount of payment must be justified. Clarify if subjects will be reimbursed for travel or other expenses.

Not applicable

There will be no payment or financial incentive for the subjects to participate. The medical device RibFx belt will be provided to the intervention group free of charge, and they will be allowed to keep the medical device upon discharge (MSRP \$125 USD).

Collaborating Sites. When research involving human subjects will take place at collaborating sites or other performance sites when UVM/UVM Medical Center is the lead site, the principal investigator must provide in this section a list of the collaborating sites and their Federalwide Assurance numbers when applicable. (agreements may be necessary)

Not applicable

Single center study at the University of Vermont Medical Center main campus (Burlington, VT). No collaborating centers or satellite/off-site locations.

INFORMED CONSENT

Consent Procedures: Describe the consent procedures to be followed, including the circumstances under which consent will be obtained, who will seek it, and the methods of documenting consent. Specify the form(s) that will be used e.g. consent (if multiple forms explain and place identifier on each form), assent form and/or HIPAA authorization (if PHI is included). These form(s) must accompany the protocol as an appendix or attachment.

Note: Only those individuals authorized to solicit consent may sign the consent form confirming that the prospective subject was provided the necessary information and that any questions asked were answered.

Consent will be obtained at the time of enrollment (during the first 24 hours of the patient's inpatient admission/observation, on their initial encounter for acute traumatic rib fracture) and consent will be obtained at the bedside by one of the members of the research team.

All documentation of consent observation/supervision will be kept in the study regulatory binder.

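### The fixed allocation sequence, with no concealment described, ends in 25 consecutive belt patients, so 25 of 35 belt patients have no concurrently enrolled control

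*Combined protocol and SAP*

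**What the plan says.** The Study Design section sets the order of assignment in words: "First 5 patients control, next 5 patients intervention, next 5 patients control, next 5 patients intervention, next 5 patients control, final 25 patients intervention". It calls this order non-randomised.

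The overview at the start of the protocol says that patients "will be assigned by the study team into either the intervention" or the control arm. Under Consent Procedures, "consent will be obtained at the bedside by one of the members of the research team". Under Recruitment, candidates are "Patients who are first identified by the clinical care team", and one exclusion criterion is a clinical judgement about pain: an additional injury causing "severe distracting pain, as determined by the admitting team". No section describes keeping the next assignment from those who screen, consent or assign. The only blinding described is that of the radiologist who grades the images.

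Statistical Considerations gives the 15 controls the task of showing change that happens without the belt, because "it should be assumed that pain will improve as time increases from the set injury point, regardless of intervention". The same section says the study is not powered between arms and offers the data for planning a definitive randomised trial. Radiological severity is to be compared between arms "to determine what differences in initial disease severity exist (so they can be accounted for". Chronic pain, opioid use and regional block are among the other variables recorded. No adjustment for enrolment order is planned.

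**The concern.** If pain falls in everyone, a pre-post fall in the belt arm cannot by itself be credited to the belt. The control arm is the plan's own guard against that reading, and the Study Design section treats the belt as the only difference between the groups. This sequence does not secure that, for two reasons.

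- **Enrolment period.** The control arm closes at the halfway point. Any change during enrolment in case mix, analgesic practice or data collection that affects recovery falls unequally on the arms.
- **Foreknowledge.** The arm is fixed by enrolment position. Staff who approach and consent patients can know it beforehand. The clinical team, which judges eligibility, is not said to be kept unaware of it. Selection by expected pain or expected tolerance of the belt is therefore possible.

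At stake are the belt-versus-control contrast and any figure taken from it to plan the later trial.

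**Working it through.** **1. Reproduce the plan's figures.** The sequence gives 5 + 5 + 5 = 15 controls and 5 + 5 + 25 = 35 belt patients, 50 in total, as stated under Number of Subjects. Statistical Considerations supplies an MPQ PRI mean of 28, SD 16, within-subject correlation 0.8 and a 20% decrease (0.2 × 28 = 5.6 points). The SD of change is 16 × √(2 × (1 − 0.8)) = 10.12. A two-sided paired t test at 0.05 then has 83% power at n = 30 and 89% at n = 35, against 83% and 88% stated. These inputs are used below.

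**2. Enrolment positions.**
- Controls are patients 1–5, 11–15 and 21–25: mean (3 + 13 + 23)/3 = 13.0.
- Belt patients are 6–10, 16–20 and 26–50: mean (5×8 + 5×18 + 25×38)/35 = 30.86.
- Belt patients after the last control: 25/35 = 71%.

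Follow-up overlaps more than enrolment does. At the protocol's 16 patients a month, three weeks covers 16 × 12/52 × 3 ≈ 11 patients. About the first 11 of the final 25 would therefore enrol while the last control is still being followed; slower accrual would make it fewer.

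**3. Bias weights for the difference in mean change (belt minus control).**
- Linear drift D from patient 1 to patient 50: (30.86 − 13.0)/49 = 0.364, so the bias is 0.36D.
- Step S after patient 25: 25/35 − 0/15 = 0.714, so the bias is 0.71S.

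The documents give no size for any drift. Assuming, for illustration, 0.25 to 0.5 SD of change:

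| Form | Bias in SD | Bias in MPQ PRI points (× 10.12) |
|---|---|---|
| Linear | 0.09 to 0.18 | 0.9 to 1.8 |
| Step | 0.18 to 0.36 | 1.8 to 3.6 |

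The points show scale only. MPQ PRI is used in the power calculation, but the trial describes collecting a 1–10 pain score and questionnaires based on the BPI and CAT.

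**4. What adjustment could recover.** Per-patient moments over the 50 positions are: variance of arm 0.7 × 0.3 = 0.21; variance of order (50² − 1)/12 = 208.25; covariance of arm and order 0.7 × (30.857 − 25.5) = 3.75. The correlation is 3.75/√(0.21 × 208.25) = 0.567.
- Unadjusted SE of the arm difference: 10.12 × √(1/35 + 1/15) = 3.12.
- SE adjusted for linear order: 3.12/√(1 − 0.567²) = 3.79, up 21%. The 95% CI half-width goes from 6.28 to 7.63.
- A step has covariance 0.15 with arm and 6.25 with order. The arm coefficient left after adjustment is (0.15 × 208.25 − 6.25 × 3.75)/(0.21 × 208.25 − 3.75²) = 7.80/29.67 = 0.26.

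Adjustment thus removes a linear drift, leaves 0.26S of a step and does nothing about selection.

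**5. Alternatives with the same 35:15.**
- Randomised 7:3 blocks of sizes 10 and 20 (20,000 simulated lists): mean position gap zero, 95% of lists within 0.06 of the span; on average 7.5 controls among patients 26–50 (95% range 6 to 9). About 8 of 50 assignments would be certain in advance even if staff knew the block sizes, against 50 of 50 now.
- Fixed order of 3 belt, 3 control, 4 belt, repeated five times: mean positions 25.0 (control) and 25.71 (belt), so the drift weight is 0.71/49 = 0.015. With 7 controls after patient 25, the step weight is 18/35 − 7/15 = 0.05.

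**The case against.** The design is declared. The protocol calls itself quasi-experimental, gives institutional improvement as its overall goal, makes the within-patient comparison the principal aim, disclaims power between arms and leaves randomisation to a later trial. The controls' stated task concerns time since injury, and 15 patients followed from admission to three weeks show natural recovery wherever they sit in the sequence. Enrolment is planned for about three months at one centre. A drift in pain level alone cancels in change scores, so recovery itself would have to change. Even the largest illustrated bias, 3.6 points, is about 1.2 standard errors (3.6/3.12) and lies inside the 6.28-point half-width.

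Much of this stands. It confines the point to the between-arm contrast and keeps the drift figures as illustrations. It does not remove the point. Low power is a matter of precision, whereas this is bias. The overview still plans to compare the belt arm with the controls. The recorded covariates cannot cover unmeasured selection or calendar change. A non-randomised design could equally well have spread its controls across enrolment. The available text gives no reason for the final run of 25; because the allocation schematic is not shown, no weight is placed on that.

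**Conclusion.** The concern holds. That 25 of 35 belt patients (71%) enrol after the last control follows directly from the written sequence and needs no assumption. The bias weights of 0.36D and 0.71S are also properties of the sequence, for a comparison of mean change between arms. The values of D and S are unknown, and neither drift nor selection has been shown to occur. Foreknowledge of the arm is possible because the order is fixed and no concealment is described; that anyone would act on it is not claimed.

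The pre-post analysis in the 35 belt patients, its stated power and the controls' description of recovery over their own follow-up are unaffected. The between-arm comparison and its value as pilot data are weakened. This should be changed because the remedy is cheap, but it does not invalidate the principal analysis.

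**What to change.** 1. **Preferred.** Keep 50 patients and 35:15. Replace the sequence with a concealed 7:3 permuted-block list mixing block sizes 10 and 20, not disclosed to recruiting staff. Open each assignment only after consent and the baseline assessment. The Procedures section already allows for this: "The initial evaluation will occur on initial assessment prior to placement of the rib belt".
2. **If randomisation is not adopted.** Spread the controls over all 50 positions, for example 3 belt, 3 control, 4 belt, repeated five times. This nearly removes the link between arm and enrolment order, but the next arm stays predictable.
3. **Failing both.** Prespecify adjustment of the arm comparison for enrolment order, and state that it does not address selection and only partly addresses a step change.

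The cost of the first option is an allocation list, an IRB amendment, consent wording on randomisation (patients are already told they may be in either arm) and a small logistic burden from interleaving the arms. Because the study is open-label, some late-block assignments remain guessable. Patient and belt numbers do not change, and neither does the principal analysis. No between-arm power is gained: it stays at about 42% for a 5.6-point MPQ PRI difference at 35:15 (SE 3.12).
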